STUDY PROTOCOL**1. STUDY INFORMATION**

Title	Effectiveness of monovalent XBB.1.5-containing Covid-19 mRNA vaccines in the Nordic countries
Protocol version identifier	1
Date of latest version of protocol	8 March 2023
EU PAS Register number	[N/A]
Medicinal products	Spikevax/Omicron XBB.1.5 Comirnaty/Omicron XBB.1.5 Comirnaty Original/Omicron BA.1 (BNT162b2) Comirnaty Original/Omicron BA.4-5 (BNT162b2) Comirnaty Original monovalent (BNT162b2) Spikevax Original/Omicron BA.1 (mRNA-1273 [/Moderna covid-19 vaccine]) Spikevax Original/Omicron BA.4-5 (mRNA-1273 [/Moderna covid-19 vaccine]) Spikevax Original monovalent (mRNA-1273 [/Moderna covid-19 vaccine]) Vaxzevria (ChAdOx1-S [/AZD1222])
Marketing authorization holder(s)	Pfizer/BioNTech Moderna AstraZeneca
Research question and objectives	The aim of this project is to evaluate the comparative effectiveness of the monovalent XBB.1.5-containing Covid-19 vaccines in preventing severe Covid-19 outcomes among individuals aged 65 years or older.
Country(-ies) of study	Denmark, Finland, and Sweden
Authors	[name]; [name]

4. ABSTRACT

Rationale and background: The Nordic countries of Denmark, Finland, and Sweden, provide a unique setting for the study of Covid-19 vaccination effectiveness. The ubiquitous nationwide demography- and health registers, which includes SARS-CoV-2 immunization and surveillance registers, allows for very large study cohorts with near real-time data availability. The monovalent XBB.1.5-containing Covid-19 vaccines were offered to the adults above 65 years of age during autumn and winter 2023-24. However, data to inform on the effectiveness are limited including when coadministered with an influenza vaccine.

Research question and objectives: The aim of this project is to evaluate the comparative effectiveness of the monovalent XBB.1.5-containing Covid-19 vaccines in preventing severe Covid-19 outcomes among individuals aged 65 years or older.

Study objectives:

1. To assess the effectiveness of monovalent XBB.1.5-containing Covid-19 vaccines for the prevention of severe Covid-19 related outcomes (Covid-19 related hospitalization or Covid-19 related death).
2. To assess waning of the effectiveness of monovalent XBB.1.5-containing Covid-19 vaccines for the prevention of severe Covid-19 related outcomes (Covid-19 related hospitalization or Covid-19 related death).
3. To assess how the effectiveness of monovalent XBB.1.5-containing Covid-19 vaccines is affected by the coadministration with an influenza vaccine.

Study design: Nationwide register-based cohort analyses in Denmark, Finland, and Sweden, during the study period from 1 October 2023 until the latest available date in 2024 at time of analyses (e.g., 29 February 2024).

Population: Source cohorts will consist of all individuals who are known residents in the three Nordic countries and have received at least four Covid-19 vaccine doses between 27 December 2020 and latest available date in 2024. The study cohorts will consist of individuals who are at least 65 years of age in Denmark, Finland, and Sweden and eligible to receive an XBB.1.5-containing Covid-19 vaccine as a fifth or sixth dose during the study period.

Variables: The outcomes of interest will be Covid-19 hospitalization and Covid-19 related death. Covariates will be variables of demography, comorbidity, and previous Covid-19 vaccination.

Data sources: Nationwide demography- and healthcare registers within each participating country.

Study size: We expect to include at least 3.1 million individuals who have received an XBB.1.5-containing Covid-19 vaccine as a 5th or 6th Covid-19 vaccine dose across the 3 Nordic countries. All available data within countries will be used and the statistical power of our proposed study will be reflected in the 95% CIs of the effectiveness estimates.

Data analysis: Using target trial emulation, we will compare individuals who received a monovalent XBB.1.5-containing Covid-19 vaccine with individuals who did not receive an additional vaccine dose in a matched survival analysis that provides comparative effectiveness estimates while considering a range of covariates.

Milestones: Study start: 8 January August 2024; study planning meeting: 22 January 2024; final first version of study protocol:12 February 2024; study report: 19 April 2024; manuscript draft: 8 July 2024.

5. AMENDMENTS AND UPDATES

Number	Date	Section	Amendment or update	Reason
1	28 February 2024	All	Page numbers added	To improve readability of the document
2	28 February 2024	9.7	Definition of index date and start of follow-up added	To provide clarification on the data analysis approach

6. MILESTONES

Milestones	Planned dates
Study start	8 January 2024
Study planning meeting	22 January 2024
Study Protocol submission (posted on EU-PAS register when approved by EMA).	12 February 2024
Registration in the EU-PAS Register	12 February 2024
Study Report submission (posted on EU-PAS register when approved by EMA).	19 April 2024
Manuscript(s) ready for submission.	8 July 2024

7. RATIONALE AND BACKGROUND

The emergence of the SARS-CoV-2 Omicron variant in late 2021 quickly raised concerns about the effectiveness of the original monovalent Covid-19 vaccines. Following the adapted bivalent Covid-19 vaccine versions targeting the Omicron BA.1 and BA.4-5 subvariants, monovalent vaccination targeting the Omicron XBB.1.5 subvariant were developed and authorized for use in the autumn and winter 2023-24 [1,2]. The XBB.1.5-containing Covid-19 vaccines have been rolled out from 1 October 2023 in Denmark, Finland and Sweden, and recommended for at-risk population groups including all people older than 65 years, in the form of a 5th or 6th Covid-19 vaccine dose, with variation across countries [3].

Evidence on the effectiveness of the monovalent XBB.1.5-containing Covid-19 vaccines is limited. However, a few studies have assessed the short-term effectiveness and immunogenicity of these vaccines. With a study period of 8 to 26 October 2023, an early report from Denmark showed a high short-term vaccine effectiveness (VE) of 76% against Covid-19 related hospitalization of the XBB.1.5-containing Covid-19 vaccines, but the average follow-up was only 9.9 days [3]. A screening method-based study conducted in the Netherlands assessed Covid-19 VE of the XBB.1.5 vaccines against hospitalization and admission to intensive care from 9 October 2023 to 5 December 2023 [4]. The study involved 2,050 hospitalized individuals older than 60 years, of whom 295 (14.4%) had received the XBB.1.5-containing Covid-19 vaccine. The VE was estimated at 70.7% (95% CI: 66.6–74.3) against hospitalization and 73.3% (95% CI: 42.2–87.6) against intensive care unit admission in the first 57 days following vaccination [4]. Another study by Link-Gelles et al. from the USA analyzed data from the Increasing Community Access to Testing SARS-CoV-2 pharmacy testing program to estimate VE for the updated XBB.1.5-containing Covid-19 vaccines, comparing receipt versus no receipt of vaccination against symptomatic SARS-CoV-2 infection [5]. The monovalent XBB.1.5-containing Covid-19 vaccines provided 54% (95% CI: 46–60%) protection against symptomatic SARS-CoV-2 infection at a median of 52 days after vaccination among adults aged ≥ 18 years [5]. Similarly, UK Health Security Agency reported incremental effectiveness of the monovalent XBB.1.5-containing vaccine at 55.4% against hospitalization 2 to 4 weeks after vaccination among those aged 65 years and older in England [6].

A randomized study by Chalkias and colleagues investigated the immunogenicity of the Moderna XBB.1.5-containing mRNA vaccine administered as a 5th dose [7]. The vaccinated population consisted of adults who previously received a primary series plus a 3rd dose of the original mRNA Covid-19 vaccine, and a 4th dose of the bivalent omicron BA.4-5-containing vaccine. The results showed that monovalent XBB.1.5-containing Covid-19 vaccine provides protection against emerging variants (XBB.1.5, XBB.1.6, XBB.2.3.2, EG.5.1, FL.1.5.1, and BA.2.86) and support the Covid-19 vaccine update to

the monovalent XBB.1.5-containing vaccine [7]. Similarly, findings by Wang et al. confirm that the XBB.1.5-containing monovalent mRNA vaccine markedly increase the magnitude of serum neutralizing antibodies against the prevalent SARS-CoV-2 Omicron subvariants such as XBB.1.5 and EG.5.1 [8].

In summary, the available evidence suggests that the XBB.1.5-containing Covid-19 vaccine can provide additional protection against Covid-19 hospitalization but data are sparse and short termed.

8. RESEARCH QUESTION AND OBJECTIVES

The aim of this project is to evaluate the comparative effectiveness of the monovalent XBB.1.5-containing Covid-19 vaccine in preventing severe Covid-19 outcomes among individuals aged 65 years or older.

Study objectives:

- 1.** To assess the effectiveness of monovalent XBB.1.5-containing Covid-19 vaccines for the prevention of severe Covid-19 related outcomes (Covid-19 related hospitalization or Covid-19 related death).
- 2.** To assess waning of the effectiveness of monovalent XBB.1.5-containing Covid-19 vaccines for the prevention of severe Covid-19 related outcomes (Covid-19 related hospitalization or Covid-19 related death).
- 3.** To assess how the effectiveness of monovalent XBB.1.5-containing Covid-19 vaccines is affected by the coadministration with an influenza vaccine.

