Statistical analysis	The Aalen-Johansen estimator will be used to obtain cumulative incidence for each treatment strategy during follow-up (with death as a competing risk). We will compare cumulative incidence across treatment strategies by risk ratios (to obtain VE) and risk differences. The Aalen-Johansen estimator will be used to estimate VE as $1 - \text{risk ratio}$ at the end of week 6 and 18 (or 24). In addition, person-time since baseline will be stratified by consecutive 6-week intervals to estimate changes in VEs per 6-week intervals; these VEs will contribute to a meta-regression estimating comparative waning. Subgroup analyses by sex (female/male), age ($</\geq 75$ years), and influenza vaccination status.	Same as for the target trial except observational analogs of per-protocol.

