Cumulative incidences will be estimated by the Aalen-Johansen estimator using death as a competing risk, and from these we will calculate the comparative VE as 1 – risk ratio at end of week 6 and 18 (or

24). The corresponding 95% CI will be calculated using the delta method. Country-specific estimates will be combined by random-effects meta-analyses implemented using the *mixmeta* package in R.

Comparative waning will be estimated using meta-regression [30]. First, we will estimate the VEs (in the specific comparison being evaluated) in each consecutive 6-week intervals (week 1-6 (day 0-42), 7-12 (day 43-84), 13-18 (day 85-126) and 19-24 (day 127-168)) by stratification on time since XBB.1.5-containing Covid-19 vaccine vaccination. Second, we will regress the VE estimates on time-since-vaccination in 6-week intervals using meta-regression in the form of an intercept and a slope coefficient. The estimated slope coefficient will represent the percentage point change in VE per 6 weeks since vaccination.

Subgroup analyses will be conducted according to sex, age groups (</≥75 years), and influenza vaccination status for XBB.1.5-containing Covid-19 vaccine vaccinated (1)co-administered on the same date, 2) received influenza vaccine within 1 weeks before to 1 week after XBB.1.5-containing vaccine dose administration but no on same date, and 3) no influenza vaccine administered within 1 weeks before to 1 week after of XBB.1.5-containing vaccine dose administration).

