We expect the majority of the study population will receive both the influenza and the XBB.1.5-containing Covid-19 vaccine on the same day, meaning that the statistical power of the subgroup analyses within populations not concurrently vaccinated will likely be lower.

Given the broad inclusion within each Nordic country, our results will likely have a high degree of generalizability to other similar populations. However, our assessment of the comparative effectiveness of monovalent XBB.1.5-containing Covid-19 mRNA-vaccines given as a fifth or sixth dose against severe Covid-19 outcomes may only indirectly support any evaluation of the effectiveness of these vaccines within other Covid-19 vaccination schedule scenarios. Our findings may similarly not directly generalize to certain subpopulations not individually studied or to populations with a

demographically different composition. Such subpopulations include for example the general population younger than 65 years old or other specific clinical subgroups that were not studied.

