12. PLANS FOR DISSEMINATING AND COMMUNICATING STUDY RESULTS

Main results expected in the final study report:

- Baseline characteristics-tables, including prior to matching and complementary matching quality diagnostics
- End of week 18 (end of week 24 if possible) cumulative incidence curves-figures for severe Covid-19 outcomes
- Vaccine effectiveness estimates tables for main analysis and influenza co-administration analyses
- Waning vaccine effectiveness figures for severe Covid-19 outcomes

We anticipate one manuscript, and findings will be reported to the general public by institutional press releases upon acceptance in academic peer-review journals or upon uploading to pre-print server (if decided relevant to do so).

We will adhere to the STROBE and ENCEPP guidelines when reporting results and drafting the manuscript(s).

Example of main results table:

	Country-combined measures of association (95% CI) at week 18/24 of follow-up				
	Contributing countries			XBB.1.5-containing vaccine vaccinated	
	Contributing countries	Events/PYRS	XBB.1.5-containing	RD	CVE

			vaccine unvaccinated		
			Events/PYRS		
Covid-19 hospitalization					
All	XX, XX, XX	XXXX/X, XXX, XXX	XXXX/X, XXX, XXX	XX (XX to XX)	XX (XX to XX)
Subgroups					
Male	XX, XX, XX	XXXX/X, XXX, XXX	XXXX/X, XXX, XXX	XX (XX to XX)	XX (XX to XX)
Female	XX, XX, XX	XXXX/X, XXX, XXX	XXXX/X, XXX, XXX	XX (XX to XX)	XX (XX to XX)
<75 years					
≥75 years					
Influenza vaccine co-administered on the same day					
Influenza vaccine administered within -/ +1 week					
No influenza vaccine administered within -/ +1 week					
Covid-19 death					
All					
Subgroups					
Male					
Female					
<75 years					
≥75 years					
Influenza vaccine co-administered on the same day					
Influenza vaccine administered within -/ +1 week					
No influenza vaccine administered within -/ +1 week					

13. References

- [1] Comirnaty: EMA recommends approval of adapted COVID-19 vaccine targeting Omicron XBB.1.5 | European Medicines Agency n.d. <https://www.ema.europa.eu/en/news/comirnaty-ema-recommends-approval-adapted-covid-19-vaccine-targeting-omicron-xbb15> (accessed January 24, 2024).
- [2] Spikevax: EMA recommends approval of adapted COVID-19 vaccine targeting Omicron XBB.1.5 | European Medicines Agency n.d. <https://www.ema.europa.eu/en/news/spikevax-ema-recommends-approval-adapted-covid-19-vaccine-targeting-omicron-xbb15> (accessed January 24, 2024).

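### Objective 3 asks whether influenza co-administration changes VE, but the protocol plans only separate VEs for three influenza levels and no estimate of the difference between them

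*Protocol*

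**What the plan says.** Section 8 of the protocol (repeated in the abstract) lists three objectives of equal rank. The third is "To assess how the effectiveness of monovalent XBB.1.5-containing Covid-19 vaccines is affected by the coadministration with an influenza vaccine".

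The analysis that corresponds to it is a subgroup analysis. The target trial table in section 9.1 closes its list of subgroups, after sex and age, with "and influenza vaccination status". Section 9.7 gives the levels, defined by "influenza vaccination status for XBB.1.5-containing Covid-19 vaccine vaccinated": same date; within one week either side but not the same date; none within one week either side. In each level VE is 1 minus the risk ratio from the Aalen-Johansen estimates. On precision, section 9.7 says "The corresponding 95% CI will be calculated using the delta method", and country results are pooled by random-effects meta-analysis.

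Section 12 promises "Vaccine effectiveness estimates tables for main analysis and influenza co-administration analyses". Its example table has one row per influenza level for each of two outcomes, with events and person-years, RD and CVE. No row or column compares levels. Section 9.8 adds one sensitivity analysis, a later start of follow-up.

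Section 9.9 expects most people to receive both vaccines on the same day and concedes that "the statistical power of the subgroup analyses within populations not concurrently vaccinated will likely be lower".

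**The concern.** Whether VE is affected by co-administration is a question of effect modification. Its answer is a contrast between levels with an interval of its own. Three VEs side by side do not supply that. A reader who wants the answer must compare rows, either by whether each CI excludes 0 or by whether the CIs overlap. Neither is a 5% comparison, and the first is most misleading when precision is unequal, which section 9.9 says to expect.

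Two things are at stake. A chance difference between rows could be taken for an effect of co-administration. And a real difference, or its absence, would have no stated estimate or interval by which it could be shown or excluded.

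**Working it through.** **1. Objectives 2 and 3 side by side.** Both are comparative. For objective 2, section 9.7 estimates VE in successive 6-week intervals and then fits a slope, described as the percentage-point change in VE per 6 weeks. That slope is a between-interval parameter. For objective 3 the same section stops at the separate VEs. Sections 9.1, 9.3, 9.7, 9.8, 9.9 and 12 contain no ratio of risk ratios, VE difference, heterogeneity test or deciding pair of levels.

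**2. How often chance alone gives a mixed picture.** The protocol has no figure to reproduce: it gives no event counts, level shares or expected VE. The following are therefore assumptions: the same true risk ratio RR = 1 − VE in all levels; independent levels; reference-arm events c for same day / within 1 week / none of 1,500/100/300, 1,500/50/150 or 600/30/80.

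- SE of log RR in a level = √(1/c + 1/(c·RR)).
- Probability that a level's 95% CI excludes 0: p = Φ(−ln RR / SE − 1.96).
- Probability that some but not all levels exclude 0 = 1 − p₁p₂p₃ − (1−p₁)(1−p₂)(1−p₃).

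Example, VE 40% and 1,500/50/150:
- SEs: √(1/1500 + 1/900) = 0.042; √(1/50 + 1/30) = 0.231; √(1/150 + 1/90) = 0.133.
- With −ln 0.6 = 0.511, p = 1.00, 0.60 and 0.97.
- Mixed picture: 1 − 1.00 × 0.60 × 0.97 ≈ 0.42.

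| True VE in every level | 1,500/100/300 | 1,500/50/150 | 600/30/80 |
|---|---|---|---|
| 30% | 39% | 71% | 87% |
| 40% | 12% | 42% | 68% |
| 50% | 2% | 19% | 44% |
| 55% | 0.6% | 12% | 33% |
| 70% | <0.1% | 1.7% | 11% |
| 76% | <0.1% | 0.7% | 7% |

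The lower three rows span roughly the hospitalization VEs cited in section 7 (55.4%, 70.7%, 76%).

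**3. The overlap rule errs the other way.** Requiring two 95% CIs not to overlap means |z| > 1.96(1 + r)/√(1 + r²), where r is the ratio of the SEs. For r = 1 the threshold is 2.77 (true two-sided error about 0.6%); for r = 4 it is 2.38 (about 1.7%). Real differences would be missed more often than a 5% comparison implies.

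**4. What a contrast would look like.** log(RRR) = log RR(same day) − log RR(none), with variance equal to the sum of the two variances. In the example, √(0.042² + 0.133²) = 0.140, and exp(1.96 × 0.140) = 1.32, so the 95% CI runs a factor of about 1.3 either side. The same-day RR alone has exp(1.96 × 0.042) = 1.09. Over the three scenarios the contrast factor is about 1.2 to 1.5 at VE 30–50%, and up to about 1.7 at VE 76%.

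**The case against.** The SAP is not shown, and a heterogeneity test or ratio column could be specified there. The table in section 12 is only an example. Both points are fair, but they do not remove the mismatch: section 9.7 fixes the levels, estimator, CI method and pooling, and gives objective 2 its comparative parameter while giving objective 3 none.

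A reader might infer that the planned table will often mislead, or that chance differences would be reported as an effect. The documents do not support that. No section says that levels will be compared by whether each CI excludes 0, and section 9.9 warns of lower power. The large percentages need assumed VEs of 30–50% and small levels. At VE 70–76% the mixed picture occurs in at most 11% of cases, and with the largest assumed counts almost never. On the other side, the VEs cited in section 7 are short-term (for example, a mean follow-up of 9.9 days in the Danish report), so week-18 values may be lower, and Covid-19 death may have fewer events.

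A reader might also compute a family-wise error rate over all pairs of levels and outcomes. That would describe tests the protocol does not contain, so it is no measure of this plan.

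Finally, the levels cover nearly separate sets of matched pairs, so a reader could approximate a contrast from the published CIs. That is true, but it would be post hoc, with no pair of levels named in advance.

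**Conclusion.** The point holds as a mismatch between objective and analysis: the protocol's stated analysis for objective 3 does not estimate the quantity the objective asks about. This follows from the text and needs no assumption.

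The risk of misreading is possible rather than established, and its size is uncertain. With equal true VE and the assumed event counts, a mixed picture arises in 2% to 87% of cases at VE 30–50% and in under 0.1% to 33% at VE 55–76%. It is small if every level has many events and VE is high, and large if a level is thin or VE is modest.

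It would go too far to conclude that a contrast with a CI settles the causal question. Section 9.7 does not match on influenza status, and the levels are defined only by the XBB.1.5-vaccinated member of each pair, so differences between levels may reflect who chooses co-administration. The contrast repairs the inference, not the comparability.

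**What to change.** In section 9.7, state that objective 3 is answered by one contrast: the ratio of risk ratios for Covid-19 hospitalization at week 18, same-day influenza vaccination versus no influenza vaccine within 1 week before or after. Compute it within each country on the log scale, with variance equal to the sum of the two level-specific log-RR variances, and pool it by the planned random-effects meta-analysis with a 95% CI.

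Show the other pairs of levels, and Covid-19 death, as exploratory ratios. Add a ratio column to the section 12 table. State that no conclusion on objective 3 is drawn from comparing separate CIs, and that the contrast may be confounded because influenza status is not a matching factor.

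The cost is one column computed from estimates already planned; no new data are needed. The downside is a wider interval than the same-day VE has (the factors in step 4 of the working), so the answer may be inconclusive. For illustration, take VE 60% with no influenza vaccine and 50% with same-day vaccination: power = Φ(ln(0.5/0.4)/√(SE₁² + SE₃²) − 1.96), where SE₁ is for same day and SE₃ for none.

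- 3,000 reference-arm events in total, 60% same day and 25% none: SEs 0.041 and 0.068, power about 80%.
- 200 events in total, 80% same day and 15% none: SEs 0.137 and 0.342, power about 9%.

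An openly wide interval for the right quantity is still preferable to leaving the comparison to the reader.

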9. RESEARCH METHODS

9.1 Study design

We will take advantage of the unique nationwide register data available to us, and construct country cohorts with individual-level information on dates of vaccination and dates of effectiveness endpoints together with relevant covariate information. All Nordic residents are assigned a unique personal identifier at time of birth or immigration, enabling linkage between registers. The three Nordic countries have universal and tax-financed healthcare systems and reporting to national registers is mandatory, providing near-complete follow-up of all residents over time. The cohort participants will be classified according to Covid-19 vaccinations received and followed up using survival analysis. We

will utilize a comparative design avoiding comparisons with unvaccinated individuals. This will reduce concern about selection bias due to inherent differences in who chooses to remain unvaccinated.

The study period will start in 1 October 2023 in the three countries. This study start date corresponds to when the XBB.1.5-containing Covid-19 vaccine was offered to the 65+ year-olds in the three countries. The study period will end on the last date of data availability at time of analyses during winter or spring 2024.

The overall research design builds on target trial emulation methodologies to estimate both relative and absolute effects. Key components of the specification and emulation of the pragmatic target trial of the effectiveness of the monovalent XBB.1.5-containing Covid-19 vaccines against severe Covid-19 using Nordic nationwide registry data are including in table below.

Protocol	Target Trial Specification	Target Trial Emulation
Eligibility criteria	
 • Aged ≥65 years in Denmark, Finland, and Sweden at start of study period (1 October 2023) • Have a known residency within the specific country at start of study period • Have received four or five Covid-19 vaccine doses (of AZD1222 and/or [original/BA4-5/BA-1 bivalent] mRNA vaccines [AZD1222 as part of the primary vaccination course only]) prior to the start of study period • No history of Covid-19 hospitalization prior to the start of study period 	Same as for the target trial.
Treatment strategies	
 1) Receive a monovalent XBB.1.5-containing Covid-19 vaccine at baseline and do not receive additional Covid-19 vaccine doses during follow-up 2) Do not receive a monovalent XBB.1.5 -containing Covid-19 vaccine at baseline and continue being unvaccinated during follow-up 	Same as for the target trial. We define the date of XBB.1.5-containing Covid-19 vaccine vaccination (that is, the index date) according to the registered date of administration.
Treatment assignment	Individuals are randomly assigned to a strategy at baseline in a 1:1 ratio	Individuals are assigned to the strategy compatible with their treatment received at that time (XBB.1.5 vaccinated and - unvaccinated); randomization is assumed conditional on matching (in a 1:1 ratio) on baseline covariates; XBB.1.5-unvaccinated are assigned the index date of the matched XBB.1.5 vaccine recipient.
Outcomes	
Covid-19 hospitalization: inpatient hospitalization with a registered Covid-19-related diagnosis and a positive PCR test for SARS-CoV-2 (within 14 days before to 2 days after the day of admission)
 
Covid-19 death: death within 30 days of a positive PCR test for SARS-CoV-2
	Same as for the target trial.

Follow-up	Follow-up for each individual will start at day 8 from treatment assignment (to ensure full immunization among XBB.1.5-containing Covid-19 vaccine recipients) and end on day of outcome event, week 18 (week 24 if possible) has passed, death, emigration, or end of the study period (date of latest data availability as of 31 March 2024), whichever occurs first.	Same as for the target trial.
Causal contrast of interest	Per-protocol	Observational analog to per-protocol effect.
Statistical analysis	The Aalen-Johansen estimator will be used to obtain cumulative incidence for each treatment strategy during follow-up (with death as a competing risk). We will compare cumulative incidence across treatment strategies by risk ratios (to obtain VE) and risk differences. The Aalen-Johansen estimator will be used to estimate VE as $1 - \text{risk ratio}$ at the end of week 6 and 18 (or 24). In addition, person-time since baseline will be stratified by consecutive 6-week intervals to estimate changes in VEs per 6-week intervals; these VEs will contribute to a meta-regression estimating comparative waning. Subgroup analyses by sex (female/male), age ($</\geq 75$ years), and influenza vaccination status.	Same as for the target trial except observational analogs of per-protocol.

